10.2 Sample size

We calculate that we will need a minimum sample size of 118 participants per vaccination group for detecting a difference between two proportions (based on seroprotection percentages for influenza A(H1N1p) of a previous study:91% vs 78% [21]) (see below), considering a 95% confidence level (two-sided) and 80% statistical power. To account for loss to follow up, we will increase sample size by 20%, so sample size will be a minimum of 142 subjects per group (Table 1).

Table 1. Sample size calculation based on published seroprotection rates for different influenza viruses

Seroprotection	P1 (AD group)	P2 (SD group)	n/per group	With additional 20%
subtypes				
Influenza A(H1N1p)	91%	78%	118	142
Influenza A(H3N2)	No information	No information		

Influenza B	No information	No information		
Where P1=percentage o	f seroprotection for AD g	roup and P2=percentage	e of seroprotection for S	D group

However, although the sample size calculation yields 142 participants per group, there may be different scenarios in which the difference between groups is shortened. In the following table, differences of 10-20% are estimated (Table 2). As a result of this calculation, it is estimated that a sample size of approximately 400 individuals per group will allow us to detect a difference of at least 10% considering a 78% seroprotection rate in the group vaccinated with non-adjuvant vaccine.

Table 2. Different scenarios in seroprotection rates (28 days post-vaccination) per group and sample size calculation

Seroprotection rate in SD group	Relative increase (5) in AD group vs SD group	n per group	Total n	With additional 20%
78%	10%	359	718	862
78%	20%	70	140	168
88g%	10%	131	262	314
88%	15%	58	116	140

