 start of the contraceptive method.
- All screening subjects will be assigned a screening subject identification number and listed in a screening log. Those subjects remaining eligible after the physical exam and evaluation of screening will be enrolled and be given a subject enrollment number prior to be immunized.

Study staff will provide participants with a copy of the informed consent as well as an informative brochure including information of the study, investigational product, and contact information of study staff and schedule of activities (Appendix D). We anticipate to recruit up to a maximum of 800 participants in the study, 400 per group. The informed consent will include permission to access medical records and link data from the previous study with data from the current study.

Subjects who fail screening may be re-screened if the Investigator thinks it is likely the subject will fulfill the inclusion/exclusion criteria requirements at a later time.

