10.8 Surveillance monitoring

An *acute illness¹* is defined as one or more of the following symptoms within the past 7 days: cough, runny nose, body aches, or feverishness (could be not measured fever). The focus of the study is on acute or newly worsened symptoms; this will be emphasized in the phrasing of screening questions, orientation to

¹Sources for this method and similar items can be found in the following manuscripts:

Irving et al. (2011) Comparison of clinical features and outcomes of medically attended influenza A and influenza B in a defined population over four seasons: 2004–2005 through 2007–2008. Influenza and Other Respiratory Viruses DOI: 10.1111/j.1750-2659.2011.00263.x

participants, and staff training. Nonetheless, participants will be discouraged from assuming they know the source of symptoms or dismissing symptoms they might attribute to allergies or non-infectious sources, since the study intends to assess all acute illnesses regardless of presumed etiology. Following are active surveillance steps.

- a. Starting at enrollment, reports of acute illness pre-season will be acknowledged by study staff but will not prompt respiratory specimen collection;
- b. During the approximately 10-20 weeks of local influenza circulation, participants will receive twiceweekly communication via cellphone messaging (e.g. *WhatsApp*) or phone call to confirm whether they have acute illness symptoms;
- c. During follow up participants will be asked to contact study staff immediately by cellphone messaging (e.g. *WhatsApp*) or telephone when they experience symptoms of acute illness; when possible, some facilities will check staff schedules to identify participants who might have missed work because of illness in order to proactively contact them;
- d. Participant reports of symptoms will be logged by study staff in a "Symptom Screening Log" (Appendix K);

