Laboratory- confirmed influenza illness rates in HCP receiving AD	Clinical	Comparison of persons who did and did not become sick with influenza after receiving the AD or SD	Person became sick with influenza after receiving AD or SD vaccine Person did not become	Nasal swab specimen tests positive for influenza by PCR	Quantitative Discrete	PCR assay (laboratory)
vaccine		vaccine	sick with influenza after receiving AD or SD vaccine	Nasal swab specimen tests negative for influenza by PCR		

Secondary Objective 6: To assess the adverse events among HCP receiving SD and AD influenza vaccines

				Criterios de	Tipo de	Instrumento de
Variable	Dimensión	Indicador	Valores	medición	variable/indicador	medición
	(Dimension)	(Indicator)	(Values)	(Measurement criteria)	(Type of variable/indicator)	(Measurement instrument)
Adverse events in HCP receiving AD vs. SD vaccine	Anticipated (Clinical)	Local reactions: pain on vaccination site, swelling, lump itching, bruising	Yes	Person had a local and/or systemic reaction(s) after receiving AD or SD vaccine	Quantitative Discrete	Post-vaccination surveillance via follow-up visits and monitoring (calls, surveys)

	AND/OR Systemic reactions: fever (≥38°C), muscle ache, joint pain, headache, malaise, fatigue, weakness, sweating, shivering	No	Person did not have a local and/or systemic reaction(s) after receiving AD or SD vaccine		
	Death, life- threatening adverse event, hospitalization or prolongation of existing	Yes	Person had a serious adverse event after receiving the AD or SD vaccine		Post-vaccination surveillance via
Serious, Unanticipated (Clinical)	hospitalization, a persistent or significant incapacity affecting normal life activities, and other unanticipated event that seriously impacts the health of participants	No	Person did not have a serious adverse event after receiving the AD or SD vaccine	Quantitative Discrete	follow-up visits, monitoring (calls, surveys), and hospitalizations

Below we describe the statistical tests that we will perform to address each primary and secondary objective, highlighting which study population will be included for each analysis. All statistical tests will be performed with a significance level of 5% and a statistical power of 80%.

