5) To evaluate laboratory-confirmed influenza illness rates in the group receiving AD influenza vaccination compared to the group receiving SD influenza vaccination. Using data collected through active surveillance, we will calculate incidence densities and use descriptive statistics and Z-test to assess differences in the proportion of HCPs who had laboratory-confirmed influenza (as determined by PCR on nasal swab samples) during the period of the clinical trial among the HCP who received the influenza vaccines AD vs. SD. A Cox regression model will be used to adjust the risk of developing influenza between both groups according to demographic and occupational characteristics. Health personnel participating in the clinical trial will be included as a study population for these analyzes.

6) To assess the adverse events among HCP receiving SD and AD influenza vaccines. Using data collected through active surveillance, we will use descriptive statistics and the Z test to assess the differences in the proportions of adverse events (anticipated and serious) between the HCP who received the AD and SD

influenza vaccines. All health personnel participating in the clinical trial will be included as a study population for these analyzes.

Table 1: Summary of Analysis by Endpoints and Analysis Populations.

OBJECTIVE	VALUATION CRITERIA	STATISTICAL TEST	POPULATION OF ANALYSIS
Primary Efficacy Analysis			
To determine if the AD influenza vaccine generates superior immunogenicity than the vaccine against SD influence without adjuvant among the HCP.	Immunogenicity - superior serumconversion of AD vaccine versus SD vaccine in HCP.	Wilcoxon signed rank test.	PP population
Secondary Efficacy Analysis			
To compare the post-vaccine immune response, in approximately 28 days after vaccination and at the end of the influenza season, among the HCP with a history of influenza infection confirmed by PCR result during any of the 6 years during the previous cohort study (2016 to 2021).	Post-vaccination immune responses, approximately 28 days after vaccination and at the end of the season, among HCPs with a history of PCR-confirmed influenza infection	Wilcoxon signed rank test.	ITTm1

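### The blanket 80% power statement in section 11.1 has no support for the comparison of PCR-confirmed influenza (secondary objective 5)

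*Combined protocol and SAP*

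**What the plan says.** Section 11.1 introduces the tests for the primary and all secondary objectives with one sentence that makes no exception: "All statistical tests will be performed with a significance level of 5% and a statistical power of 80" per cent.

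For secondary objective 5 the same section plans incidence densities, descriptive statistics, a Z-test of "differences in the proportion of HCPs who had laboratory-confirmed influenza", and an adjusted Cox model. The summary table of analyses at the end of 11.1 lists descriptive statistics, incidence densities and the Cox model for this objective, but not the Z-test.

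The only power work is in section 10.2. It is "based on seroprotection percentages for influenza A(H1N1p) of a previous study:91% vs 78" per cent, "considering a 95% confidence level (two-sided) and 80% statistical power". A second table there leads to the planned size: "it is estimated that a sample size of approximately 400 individuals per group will allow us to detect a difference of at least 10" per cent, from 78% seroprotection in the SD group.

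The data for objective 5 come from the 2022 season alone (section 2). Recruitment is "up to a maximum of 800 participants in the study, 400 per group" (section 10.4). Illness reported before the season does not lead to a swab. Active case finding runs "During the approximately 10-20 weeks of local influenza circulation" (section 10.8). Both arms receive an influenza vaccine.

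**The concern.** A significance level can be fixed for every test in a plan. Power cannot, because it depends on the endpoint's event rate, the size of effect sought and the number of participants. The 400 per group was derived from seroprotection, where 78% or more of each arm is expected to meet the endpoint. PCR-confirmed influenza in one season among vaccinated staff is a different endpoint, and the plan states none of the quantities needed to work out its power.

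What is at stake is how a non-significant result would be read. Someone who takes section 11.1 at its word would treat it as a negative finding from a test with 80% power, when the interval around it could be wide enough to include a clear benefit or a clear disadvantage.

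**Working it through.** **1. Reproduce the plan's own figure.** Section 10.2 gives 118 per group for 91% vs 78% (two-sided 5%, 80% power). With unpooled variance:

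n = (1.960 + 0.842)² × [0.91×0.09 + 0.78×0.22] / 0.13² = 7.849 × 0.2535 / 0.0169 = 117.7, so 118.

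Increasing this by 20% gives 118 × 1.2 = 142. The same formula with 86% vs 78% gives the 359 in Table 2. The stated sizes are therefore reproduced, and all of them are for seroprotection.

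**2. Inputs for objective 5.** From the documents: 400 per arm, 1:1 allocation, two-sided 5%, Z-test on proportions. Not in the documents, so assumed here: SD attack rate p and AD/SD risk ratio RR.

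**3. Power of the Z-test.** With p₁ = p, p₂ = RR × p, p̄ = (p₁ + p₂)/2, d = p₁ − p₂:

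s₀ = √[2p̄(1 − p̄)/400], s₁ = √{[p₁(1 − p₁) + p₂(1 − p₂)]/400}

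Power = Φ[(d − 1.96 s₀)/s₁] + Φ[(−d − 1.96 s₀)/s₁]

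Example, p = 5%, RR = 0.7: p₂ = 3.5%, p̄ = 4.25%, s₀ = 0.01426, s₁ = 0.01425. The first term is Φ[(0.015 − 0.02796)/0.01425] = Φ(−0.909) = 0.182. The second is about 0.001. Power is 18.3%.

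| Assumed SD attack rate | RR 0.8 | RR 0.7 | RR 0.5 | Total cases at RR 0.7 |
|---|---|---|---|---|
| 1% | 6.0% | 7.5% | 13.0% | 7 |
| 2% | 7.1% | 10.1% | 21.4% | 14 |
| 5% | 10.5% | 18.3% | 46.1% | 34 |
| 10% | 16.7% | 33.0% | 76.7% | 68 |
| 15% | 23.7% | 47.9% | 92.0% | 102 |
| 20% | 31.3% | 61.8% | 97.8% | 136 |

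Total cases = 400 × p × (1 + RR). At the smallest rates the approximation is rough: simulation of the Z-test gave 5.3% at 1% and RR 0.8, and 77.8% at 10% and RR 0.5.

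**4. Where 80% is reached.** With 400 per arm, the SD attack rate needed is about 49% for RR 0.8, 28% for RR 0.7, 17% for RR 0.6 and 11% for RR 0.5. If the plan's 20% loss left 320 per arm contributing data (a worst case), these become about 55%, 33%, 20% and 13%.

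**5. Cox model.** Events needed = 4 × 7.849 / (ln HR)²: 631 for HR 0.8, 247 for 0.7, 66 for 0.5. At a 10% SD rate the expected totals are 72, 68 and 60. The model does not change the picture.

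**6. Precision.** With 5% in each arm (20 cases each), the standard error of the log risk ratio is √[2 × 0.95/20] = 0.308. The 95% confidence interval around a ratio of 1 is exp(±1.96 × 0.308), or 0.55 to 1.83.

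**The case against.** The strongest reply is that power for objective 5 is conditional, and some plausible-looking inputs do give 80%. If illness risk followed the share not seroprotected in Table 1 (22% vs 9%, a ratio of 0.41), an SD attack rate of about 7.5%, or about 42 cases in total, would be enough. That stands. It rules out two stronger readings that a reader might infer: that the season will yield too few cases, and that the 80% figure is false for this objective. The documents give no attack rate or target effect from which to show either. The link from seroprotection to illness is itself an assumption that the plan does not make. The Table 2 scenario (22% vs 14% not seroprotected, a ratio of 0.64) would need an SD rate of about 20%.

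A second reply is that objective 5 is secondary, is worded as an evaluation of rates, and already has incidence densities and descriptive statistics planned. That also stands, and it narrows the remedy. What is missing is a stated confidence interval and an honest account of power. The Z-test's absence from the summary table does not help, because the text of 11.1 still plans it and the 80% sentence covers all tests.

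A third reply is that the sentence merely repeats the design parameters of section 10.2. That may be the intent, but it is not what the sentence says.

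A reader might also infer that the plan invites health authorities to act on a null illness result, or that using one season is a design error. Neither is supported. Section 9 is conditional on the hypothesis, which concerns immunogenicity, and no equal-protection conclusion is planned. One season is a normal feature of an immunogenicity trial with illness surveillance as a secondary element.

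**Conclusion.** The point holds as a matter of unsupported wording. The 80% in section 11.1 is backed only by the seroprotection calculation in section 10.2; nothing in the plan backs it for objective 5. Across assumed SD attack rates of 1-10% and risk ratios of 0.5-0.8, every combination falls short of 80%, with power from about 6% to 77%. Larger rates combined with larger effects do pass 80%. These ranges are assumptions, and the calculation takes the full 400 per arm as contributing data. The primary conclusion is unaffected.

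**What to change.** In section 11.1, keep the 5% significance level for all tests, but limit the 80% statement to the seroprotection comparison sized in section 10.2.

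For objective 5, state that the comparison was not sized. Report incidence rates by arm and a risk or hazard ratio with its 95% confidence interval. Add a short table of power, or of the detectable ratio, over a range of assumed attack rates. For example, with 400 per arm the ratio detectable with 80% power is about 0.30 at a 5% SD rate, 0.48 at 10% and 0.57 at 15%. A non-significant result would then not be read as a null from an 80%-powered test.

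The cost is an edit to the protocol and SAP text, with no new participants, samples or visits. The downside is that the stated power for objective 5 becomes less favourable.

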10.5 Allocation of subjects

We will randomly allocate consented subjects to either receive standard or adjuvanted influenza vaccination following a blocked randomization methodology to balance the number of participants in two study arms [24]. The electronic data capture system that will be used named REDCap, includes a tool that will allow randomization.

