10.13 Study outcomes

The primary outcome to be measured will be seroconversion at day 28 after vaccination. Seroconversion will be defined as having a haemagglutination inhibition (HI) geometric mean titre (GMT) of \geq 1:40 in the case the pre-vaccination HI GMT <1:10 or having a four-fold rise in titre in the case the pre-vaccination HI GMT \geq 1:10. We will also measure HI GMT at the end of season. Seroprotection will be defined as having an HI GMT \geq 1:40.

Other outcomes that will be measured include:

-reactogenicity to vaccination

-acceptability of AD influenza vaccination

-acute respiratory illness (ARI)

-ARI-associated outcomes (absenteeism, medical visits, hospitalization, other)

-laboratory-confirmed influenza and other respiratory pathogens

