11. ANALYSIS

11.1 Data analysis

Baseline data will be described and analyzed for group comparison, as a check on the adequacy of randomization procedures. Table 3 includes the dependent variables for the primary objective and the first 4 secondary objectives, including the evaluation criteria for each one (Table 3), while tables 4 and 5 detail the dependent variables for secondary objectives 5 and 6, accordingly.

Primary objective: To determine if AD influenza vaccine generates superior immunogenicity than the nonadjuvanted SD influenza vaccine, at approximately 28 days after vaccination and at the end of season, among HCP.

				Criterios de	Tipo de	Instrumento de
	Dimensión	Indicador	Valores	medición	variable/indicador	medición
Variable	(Dimension)	(Indicator)	(Values)	(Measurement criteria)	(Type of variable/indicator)	(Measurement instrument)
Immunogenicity of AD and SD vaccines among health care workers	Seroconversion (Clinical)	Comparison of HI [*] GMT [†] of serum collected at Day 28 (post- vaccination specimen) and at the end of the influenza season (end of season specimen) to serum collected at Day 0 (pre- vaccination specimen) for each vaccine (AD and SD)	Person seroconverted following vaccination Person did not seroconvert following vaccination	Post- vaccination/end of season HI GMT \geq 1:40 if pre-vaccination HI GMT <1:10 OR 4-fold rise in post- vaccination/end of season HI GMT if pre- vaccination HI GMT \geq 1:10 Post- vaccination/end of season HI GMT <1:40 if pre-vaccination HI GMT <1:10 OR <4-fold rise in post- vaccination/end of season HI GMT if pre- vaccination HI GMT \geq 1:10	Quantitative Continuous	Haemagglutination inhibition assay (laboratory)
	Seroprotection (Clinical)		Person is seroprotected following vaccination	Post- vaccination/end of season HI GMT ≥1:40	Quantitative Continuous	Haemagglutination inhibition assay
			Person is not seroprotected	Post- vaccination/end of season		

	following	HI GMT <1:40	
	vaccination		

*HI = haemagglutination inhibition

[†]GMT = geometric mean titer

Secondary Objective 5: To evaluate laboratory-confirmed influenza illness rates in the group receiving AD influenza vaccination compared to the group receiving SD influenza vaccination.

Variable	Dimensión	Indicador	Valores	Criterios de medición	Tipo de variable/indicador	Instrumento de medición
	(Dimension)	(Indicator)	(Values)	(Measurement criteria)	(Type of variable/indicator)	(Measurement instrument)

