Primary objective: To determine if AD influenza vaccine generates superior immunogenicity than the nonadjuvanted SD influenza vaccine, at approximately 28 days after vaccination and at the end of season, among HCP. We will use Wilcoxon signed-rank tests to assess HI GMT differences and differences in proportions of HCP who seroconverted and were seroprotected between AD and SD vaccination groups. All HCP included in the clinical trial will be included as the study population for these analyses.

Secondary objectives:

1) To compare immune responses post-vaccination, at approximately 28 days after vaccination and at the end of season, among HCP with a history of PCR-confirmed influenza infection during any of the six cohort years (2016 to 2021). The outcome variables will be the same as those of the primary objective matrix of variables, but dividing the enrolled study population to include only the HCP with a history of PCR-confirmed influenza infection during any of the six-year cohort (2016-2021). We will use Wilcoxon signed-rank tests to assess HI GMT differences and differences in proportions of HCP who seroconverted and were seroprotected between AD and SD vaccination groups. Only HCP in the clinical trial with a history of PCR-confirmed influenza infection during any of the six cohort years (2016 to 2021) will be included as the study population for these analyses.

2) To compare immune responses post-vaccination, at approximately 28 days after vaccination and at the end of season, among HCP with no history of PCR-confirmed influenza infection during the six cohort years (2016 to 2021), among those with data available for the six cohort years. The outcome variables will be the same as those of the matrix of variables in the primary objective, but dividing the enrolled study population to include only the HCP with no history of PCR-confirmed influenza infection during any of the six-year cohort (2016-2021). We will use Wilcoxon signed-rank tests to assess HI GMT differences and differences in proportions of HCP who seroconverted and were seroprotected between AD and SD vaccination groups. Only HCP in the clinical trial with no history of PCR-confirmed influenza infection during any of the six cohort years (2016 to 2021) will be included as the study population for these analyses.

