To compare the post-vaccine immune response, in approximately 28 days after vaccination and at the end of the influenza season, among the HCP who did not have a history of influenza infection confirmed by PCR result during any of the 6 years during the previous cohort study (2016 to 2021); among those with information available during the 6- year cohort.	Post-vaccination immune responses, at approximately 28 days after vaccination and at the end of the season, among HCPs with no history of PCR- confirmed influenza infection.	Wilcoxon signed rank test.	ITTm2
Examine whether the number of prior vaccinations against influenza during the previous 10 years, as documented in the medical records, modifies the immune response after receiving the AD or SD vaccine in approximately 28 days after vaccination and at the end of flu season.	Immune responses after receiving the AD or SD influenza vaccine, approximately 28 days after vaccination and at the end of the season	Descriptive statistics: multivariable logistic regression model	ITTm
Analyze and identify risk factors for a suboptimal response (lack of seroconversion / sero protection) to standard dose (SD) and / or adjuvanted (AD) influenza vaccines	Risk factors for suboptimal response (lack of seroconversion / seroprotection)	Descriptive statistics. Generalized linear models (GLM) with Poisson or binomial functions as appropriate	ITTm

To assess rates of laboratory-confirmed influenza illness in the group that received the AD adjuvanted influenza vaccine compared to the group that received the standard dose SD influenza vaccine.	Laboratory confirmed influenza illness rates among HCP receiving influenza vaccines AD vs. SD	Descriptive statistics., Calculation of incidence densities. Multivariate Cox Regression Model.	ITTm
Security Analysis			
To assess adverse events among HCP who received SD and	Frequency of AE	Descriptive statistics and	Security
AD influenza vaccines		Z test to evaluate	Population
		differences in	
		proportions	

- Population by Protocol: All HCPs vaccinated with any of the research products.
- ITTm population: HCPs who, having been vaccinated, became ill and did not become ill with influenza after receiving the AD or SD vaccine.
- ITTm1 population: HCPs may, having been vaccinated, became ill with influenza after receiving the AD or SD vaccine at approximately 28 days after vaccination and at the end of the season.

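### The primary AD-versus-SD comparison, and secondary objectives 1 and 2, name a paired test (Wilcoxon signed-rank) although the arms are independent and no pairing is defined

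*Combined protocol and SAP*

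**What the plan says.** Section 11.1 (Data analysis) gives the same sentence three times, under the primary objective and under secondary objectives 1 and 2. It proposes "Wilcoxon signed-rank tests to assess HI GMT differences and differences in proportions of HCP who seroconverted and were seroprotected between AD and SD" vaccination groups. The summary table of analyses at the end of 11.1 agrees. Its primary row gives the criterion as "superior serumconversion of AD vaccine versus SD vaccine in HCP" and the test as "Wilcoxon signed rank test", and the rows for secondary objectives 1 and 2 name the same test.

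Other parts of the plan describe a two-sample problem:

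- **Allocation (10.5):** subjects are allocated "following a blocked randomization methodology to balance the number of participants in two study arms". The study summary (section 2) states 1:1 randomisation to a single dose of one vaccine or the other.
- **Primary outcome (10.13):** "The primary outcome to be measured will be seroconversion at day 28 after vaccination", which is yes or no for each person.
- **Sample size (10.2):** calculated "for detecting a difference between two proportions".
- **Other AD-versus-SD proportions (11.1):** for objective 5 the plan will "use descriptive statistics and Z-test to assess differences in the proportion of HCPs who had laboratory-confirmed influenza", and objective 6 uses a Z-test for adverse events.

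The variable table for the primary objective types both seroconversion and seroprotection as "Quantitative Continuous".

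**The concern.** The signed-rank test ranks the differences within pairs. Here one member of each pair would have to be an AD recipient and the other an SD recipient, and nothing in the plan says who is paired with whom. Blocking serves only to balance arm sizes and creates no pairs. The one natural pairing is each person's Day 0 serum with the same person's later serum. The variable table uses it to define seroconversion within each vaccine. A signed-rank test on those pairs would ask whether titres rose in an arm, not whether AD is better than SD.

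The analyst therefore has two options. One is to invent a pairing, and drop people from the larger arm if the arms differ in size. The other is to substitute a test that the plan does not name for this comparison. Either way, the test behind the superiority claim would be chosen after the plan was written, possibly with the data in view.

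**Working it through.** **1. The plan's own figure.** Section 10.2 gives 118 per group for 91% versus 78%, two-sided 5%, power 80%. The unpooled formula for two independent proportions is

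n = (1.960 + 0.8416)² × [0.91×0.09 + 0.78×0.22] / 0.13² = 7.849 × 0.2535 / 0.0169 = 117.7, rounded up to 118.

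118 × 1.2 = 141.6, rounded up to 142, as stated. The design calculation is thus for independent arms.

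**2. Can the arms be paired at all?** Section 10.4 plans 400 per group and 10.2 allows 20% for loss, giving 400 × 0.8 = 320 evaluable per arm on average. If losses are independent (assumption), P(unequal arms) = 1 − Σ P(X = k)², with X ~ Binomial(400, 1 − loss).

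| Loss | P(unequal arms) |
|---|---|
| 5% | 93.5% |
| 10% | 95.3% |
| 20% | 96.5% (mean gap 9 people) |

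**3. Equal arms: does the pairing matter?** For 0/1 outcomes, with zero differences dropped, the signed-rank statistic reduces to z = (b − c)/√(b + c), where b and c count the discordant pairs. Take 130/320 versus 106/320 (illustrative). If k pairs have both members positive, then b = 130 − k, c = 106 − k and z = 24/√(236 − 2k). The numerator is fixed, but the denominator depends on the pairing.

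- k = 35: z = 24/√166 = 1.863, p = 0.062
- k = 43: z = 24/√150 = 1.960, p just above 0.050
- k = 51: z = 24/√134 = 2.073, p = 0.038

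Under random pairing k is hypergeometric with mean 130 × 106/320 = 43.1, almost exactly at the threshold. The two-sample Z-test gives a single answer: 0.075/√(0.36875 × 0.63125 × 2/320) = 0.075/0.03814 = 1.966, p = 0.049.

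| Data (illustrative) | Z-test p | Signed-rank p, 2.5th–97.5th percentile over random pairings | Pairings with p < 0.05 |
|---|---|---|---|
| 130/320 v 106/320 | 0.049 | 0.038–0.062 | 46% |
| 269/320 v 250/320 | 0.055 | 0.042–0.069 | 19% |
| 131/324 v 104/315, 9 people dropped at random | 0.052 | 0.029–0.094 | 39% |
| 275/320 v 250/320 | 0.010 | 0.007–0.015 | essentially all |

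**4. How often would the verdict depend on the pairing?** A trial is counted if between 2.5% and 97.5% of its random pairings give p < 0.05 (3,000 simulated trials per setting, 320 per arm).

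- No difference (33%, 50% or 78% in both arms): 2–3% of trials
- Power of 55–82% (41% v 33%, 44% v 33%, 86% v 78%): 6–9%
- The plan's 91% v 78%: 0.3%

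**5. Error rates with equal arms and random pairing** (20,000 simulated trials per setting). Type I error is 4.9–5.2% for signed-rank and 4.9–5.5% for the Z-test. Power at 86% v 78% is 75.0% and 75.1%.

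**6. Titres.** One borderline data set was simulated for each assumed log2 SD (mean 6, rounded to 2-fold steps, rank-sum p about 0.050), with 2,000 random pairings each. The signed-rank p ran over 0.040–0.137 (SD 1.5), 0.021–0.084 (SD 2.0) and 0.039–0.132 (SD 2.5).

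**The case against.** The strongest reply is that this is a naming slip: signed-rank was written for rank-sum and copied forward. Reading rank-sum throughout would give one reproducible p-value for titres and for both proportions, with equal or unequal arms. On 0/1 data the tie-corrected rank-sum test is practically the pooled Z-test: for 130/320 versus 106/320 it gives 0.0494 against 0.0493. This stands, and it means that a one-word correction would cure the core defect. It does not show that the plan is sound as written. All six places name the paired test, nothing corrects them, and the plan's stated method for other AD-versus-SD proportions is a Z-test, so a reader cannot tell which test is meant.

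It can also be said that the practical effect is small, that the borderline data sets were chosen to sit near 0.05, and that in reality an analyst would simply switch to a two-sample test. All of this is fair. The p-value ranges show that the result is not unique; they do not predict how often the verdict would be wrong. The switch itself is the problem, because the plan does not say which test replaces the named one.

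Finally, the Z-test precedent is slightly uneven: for objective 5 it appears in the text but not in that objective's summary-table row. For objective 6 it appears in both.

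**Conclusion.** The concern holds. The pre-specified primary test, and the tests for secondary objectives 1 and 2, do not fit the design and cannot be run as written without an arbitrary pairing. Unequal evaluable arms are close to certain (93.5–96.5% for 5–20% loss), so some participants would also have to be dropped. The two infection-history subgroups are further exposed, because no stratification by infection history is stated.

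The harm is a primary analysis that is undefined and not reproducible. It is not an inflated error rate: with equal arms type I error stays near 5%, power is nearly the same, the sample size stands, and clear results do not change.

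The 78% and 91% rates are the plan's, and they are for seroprotection rather than the seroconversion endpoint. The other rates, the loss pattern and the titre distributions are assumptions. The conclusion does not depend on them, since it follows from the absence of any defined pairing. Because it concerns the primary test, it must be corrected.

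**What to change.** In section 11.1 (primary objective and secondary objectives 1 and 2) and in the three matching rows of the summary table, replace the signed-rank test as follows:

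- **Seroconversion and seroprotection:** the two-sample Z-test of proportions already planned for objectives 5 and 6 (equivalent to the uncorrected chi-square test), reporting the AD minus SD difference with a 95% confidence interval.
- **HI titres:** a two-sample comparison of log titres, reported as a GMT ratio with a 95% confidence interval, with the Wilcoxon rank-sum test as the non-parametric check.

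The minimum that removes the defect is to write rank-sum for signed-rank in all six places. The version above is preferable because it matches the plan's other comparisons of proportions and its GMT measure, and it gives an effect estimate.

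As a tidy-up, re-type seroconversion and seroprotection as binary in the variable table.

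The cost is SAP wording only, with no new data and no change to the sample size. The change should be made before unblinding so that the replacement is still pre-specified.
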